All training will be documented using training records including the elements of training completed, the trainers that delivered the training and the signatures of the participants. Site initiation visits or conference calls may be made by a Sponsor-appointed Monitor to review the Study Protocol and documentation requirements with the Investigator and clinic support staff involved in the study. The Sponsor will then determine if additional center-specific training is needed and will ensure that all researchers involved in the project have adequate training. Study activities may only be performed once the Sponsor confirms activation of the investigational site.

In addition to training, at a minimum, the following documentation must be in place at the investigational site before patient enrollment begins:

- Current Investigator's and Sub-Investigator's CVs
- Signed study agreement
- Completed training in human research subject protection or an overview of Good Clinical Practice if required by the IRB.
- IRB approval letter for the Study Protocol and amendment(s)
- Patient Informed Consent approved by both the IRB and Otto Bock Healthcare Products GmbH

Adverse Events

Adverse Event Definition

An adverse event is any untoward medical occurrence in a patient. An underlying disease or symptoms associated with the underlying disease that were present prior to the fitting of study devices are not reportable. However, any increase in severity of the underlying disease or symptoms since a study fitting is to be reported as an adverse event. If an adverse event leads to multiple outcomes that sequentially worsen during the course of the study, the worst event is reported. For example, skin irritation leading to a wound infection would be reported as infection.

Adverse Event Reporting

Once a subject is enrolled, all adverse events must be reported until the subject is withdrawn or is terminated from the study.

Adverse Event Adjudication

Events will be adjudicated per the definitions below.

Serious Adverse Event

A Serious Adverse Event (SAE) is an Adverse Event that:

1. led to a death;
2. led to a serious deterioration in the health of the patient that
 - results in a life-threatening illness or injury;
 - results in a permanent impairment of a body structure or a body function;
 - requires hospitalization or prolongation of existing hospitalization;

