 - results in medical or surgical intervention to prevent permanent impairment to body structure or a body function; or
3. led to fetal distress, fetal death or a congenital abnormality or birth defect.

Relatedness

Each adverse event will be assessed regarding relatedness to the study device or the fitting procedure. In addition, the level of relatedness will be classified according to definitions as presented in Table 3.

Table 3 Rating the Relatedness of Adverse Events

Relatedness:	Description:
Highly Probable	The adverse event follows a reasonable temporal sequence from receipt (or attempted receipt) of the device treatment or procedure.
Probable	The adverse event follows a reasonable temporal sequence from receipt of the device treatment or procedure and the possibilities of factors other than the device treatment or procedure, such as underlying disease, concomitant drugs, or concurrent treatment can be excluded.
Possible	The adverse event follows a reasonable temporal sequence from receipt of the device treatment or procedure and the possibility of device treatment or procedure involvement cannot be excluded. However, other factors such as underlying disease, concomitant medications, or concurrent treatment are presumable.
Unlikely	The adverse event has an improbable temporal sequence from receipt of the device treatment or procedure, or it can be reasonably explained by other factors, including underlying disease, concomitant medication, or concurrent treatment.
Not Related	The adverse event has no temporal sequence from receipt of the device treatment or procedure, or it can be explained by other factors, including underlying disease, concomitant medication, or concurrent treatment.

Severity Rating

The severity of adverse events will be classified according to definitions as presented in Table 4.

Table 4 Rating of the Severity of Adverse Events

Severity:	Description:
Mild	Usually transient, requiring no special treatment, does not interfere with the patient's daily activities.
Moderate	Low-level inconvenience or concern to the patient, may interfere with daily activities, usually resolved by simple therapeutic non-interventional methods.
Severe	Interruption in patient's daily activity requiring systemic drug therapy or other treatment.

Statistical Considerations and Data Analysis**Sample Size**

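### In Table 3 the top relatedness grade, Highly Probable, has a weaker test than Probable or Possible; Unlikely and Not Related also overlap, and no precedence rule is given

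*Combined protocol and SAP*

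**What the plan says.** The Adverse Event Adjudication section makes the written definitions the rule: "Events will be adjudicated per the definitions below". The Relatedness section then describes two steps. First, "Each adverse event will be assessed regarding relatedness to the study device or the fitting procedure". Second, "In addition, the level of relatedness will be classified according to definitions as presented in Table 3".

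Table 3 has five rows:

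- *Highly Probable*: "The adverse event follows a reasonable temporal sequence from receipt (or attempted receipt) of the device treatment or procedure". The row ends there.
- *Probable*: the same timing, and other factors "such as underlying disease, concomitant drugs, or concurrent treatment can be excluded".
- *Possible*: the same timing, and "the possibility of device treatment or procedure involvement cannot be excluded". The row adds: "However, other factors such as underlying disease, concomitant medications, or concurrent treatment are presumable".
- *Unlikely*: improbable timing, or a reasonable explanation by other factors.
- *Not Related*: no temporal sequence, or an explanation by other factors.

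The protocol gives no order of precedence among the rows and does not say which grades make an event device-related. The primary safety objective (Clinical Study Summary; Objectives, Safety) is to describe device-related adverse events, together with stumbles and falls, by frequency and severity. Reporting does not depend on the grade: "Once a subject is enrolled, all adverse events must be reported".

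**The concern.** A graded causality scale should ask for more evidence as the grade rises, and each event should fit one row. Here the highest grade asks for the least of the three grades that need reasonable timing, and the two lowest grades can both be met by one event. Two adjudicators who each follow the text could record different grades for the same event, and neither would be wrong.

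The descriptive safety summary is at stake. If relatedness grades are tabulated, their distribution depends on how the adjudicator resolves the overlap. If the grades are also used to decide which events are device-related, the count under the primary safety objective may depend on it too.

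**Working it through.** No sample size, power or alpha figure is involved. The check sets the rows side by side and asks which can be met by one event.

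| Grade | Timing | Other factors | Device involvement |
|---|---|---|---|
| Highly Probable | reasonable | no condition | no condition |
| Probable | reasonable | excluded | no condition |
| Possible | reasonable | presumable | cannot be excluded |
| Unlikely | improbable, **or** → | reasonably explain the event | no condition |
| Not Related | none, **or** → | explain the event | no condition |

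**Top three rows.** Write T for reasonable timing, X for other factors excluded, P for other factors presumable, and D for device involvement that cannot be excluded. Then:

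- Highly Probable = T
- Probable = T and X
- Possible = T and P and D

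Adding conditions to T can only narrow the set, so *Probable* and *Possible* both lie wholly inside *Highly Probable*. *Probable* and *Possible* do not overlap each other, since X and P exclude one another. The fault is in the top row.

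**Bottom two rows.** Take an improbably timed event that other factors explain. It meets *Unlikely* by its timing and *Not Related* by its explanation. This does not depend on whether the word that separates the two explanation clauses marks a real difference.

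**Listing the cases.** Cross timing (reasonable, improbable, none) with other factors (excluded, presumable only, explaining) and device involvement (can or cannot be excluded): 3 × 3 × 2 = 18 combinations. Treat the two explanation clauses as one test. The combinations that meet more than one grade are:

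- reasonable timing, factors excluded: 2
- reasonable timing, factors presumable, device not excluded: 1
- reasonable timing, factors explaining: 2
- improbable timing, factors explaining: 2
- no temporal sequence, factors explaining: 2

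The total is 2 + 1 + 2 + 2 + 2 = 9 of 18. Three of the 18 have both the device and other factors excluded, which is not coherent, and one of these is among the 9. Without them the figure is 8 of 15. These counts depend on how the wording is coded and are not event frequencies. The two nestings follow from the text alone.

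**Effect on a device-related count.** Take a well-timed event with other factors presumable and device involvement not excluded. It meets both *Highly Probable* and *Possible*, which are two grades apart. If *Possible* and above count as device-related, the event is counted either way and only the tabulated level changes. If the cut-off is *Probable* and above, it is counted under one grade and not under the other. The *Unlikely* and *Not Related* overlap changes the count only if *Unlikely* is counted as related. The protocol gives no cut-off, so none of these cases can be ruled out.

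**The case against.** The best defence is that the labels carry the order. An adjudicator who sees *Highly Probable* above *Probable* will assume that the top grade needs at least as much evidence, and will settle most cases sensibly. The Relatedness section also has a separate first assessment, which may be what supplies device-related status, with Table 3 adding only degree. The Data Analysis section names severity as its example of an ordinal adverse event variable and does not mention relatedness. The study is a feasibility study of up to 30 subjects with a primarily descriptive analysis.

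Much of this stands, and it rules out three stronger readings that a reader might infer:

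- *The whole scale is unordered.* The documents do not support this. From *Probable* down to *Not Related* the rows descend plausibly; the order fails only at the top.
- *One event would be graded at both ends of the scale.* Read as bare logic, a well-timed event explained by other factors does satisfy both *Highly Probable* and *Not Related*. But to give the top grade to an event explained by underlying disease, an adjudicator would have to ignore the label altogether. The text does not make that a realistic risk.
- *The primary safety count is wrong.* This cannot be concluded, because the first assessment may decide device-relatedness without Table 3.

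The defence does not remove the point. The protocol makes the definitions the adjudication rule, not the labels. The doubt is also not confined to neighbouring grades: *Possible* and *Highly Probable* overlap, and an event with other presumable causes is one on which careful adjudicators may differ.

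**Conclusion.** The defect is real and lies in the wording. *Highly Probable* omits the exclusion of other factors that the next grade down requires, so it contains both *Probable* and *Possible*. *Unlikely* and *Not Related* overlap, and no precedence rule resolves either problem.

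The consequence is limited. Any descriptive summary by relatedness grade could be distorted. The effect on the primary safety count is conditional: it arises only if the grades decide what is device-related, and then only for some cut-offs. The number of affected events cannot be estimated, because the documents give no event rate. All adverse events are reported whatever their grade, and severity and seriousness have their own definitions. No efficacy result, sample size or interim decision changes.

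This rests on the *Highly Probable* row being complete as printed. It ends as a full sentence, and nothing suggests that text was lost.

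**What to change.** 1. Make *Highly Probable* at least as strict as *Probable*: reasonable timing and other factors excluded, plus a distinguishing condition chosen by the sponsor. Alternatively, merge the two grades.
2. Reword *Unlikely* and *Not Related* so that they differ, for example device involvement not fully excluded against device involvement excluded.
3. Add one precedence sentence so that each event gets exactly one grade. It is still needed after step 2, because *Possible* also refers to device involvement that cannot be excluded.
4. In the same change, state which grades count as device-related and how this links to the first relatedness assessment. Do this before the data are reviewed.

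One check on the rewording: a well-timed event with other factors presumable but not explaining it, and with device involvement excluded, now meets only *Highly Probable*. Tightening that row would leave it ungraded unless *Not Related* covers excluded device involvement, as the example in step 2 does.

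The cost is a minor protocol amendment, with the written approval that the Institutional Review Board section requires for protocol modifications, and a brief update to site training. No extra visits or subjects are needed.

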The six-minute walk test is performed as an objective evaluation of functional exercise capacity. The six-minute walk test is easy to administer, well tolerated, and typically reflective of activities of daily living. The test measures the distance that the patient can walk on a flat, hard surface, indoors, in a period of six minutes. The walk test is patient self-paced and assesses the level of functional capacity. Patients are allowed to stop and rest during the test, however, the timer does not stop. If the patient is unable to complete the time, the time stopped is noted and the reason for stopping prematurely is recorded. When administering the six-minute walk test, the recommendations of the American Thoracic Society will be followed (ATS Statement, 2002), which requires systolic blood pressure to be below 180 mm Hg and heart rate to be below 120 bpm prior to the test.

Before and immediately after the test, the Borg Rating of Perceived Exertion (RPE) using the CR100 (centiMax) scale (Borg 2002) will be measured.

Prior to the test, all subjects will wear a heart rate strap, and after the test the recorded heart rate will be collected.

Trinity Amputation and Prosthesis Experience Scales (TAPES)

The TAPES is a quality of life measure with nine subscales that broadly fall into three domains: Psychosocial, Activity Restriction, and Satisfaction with the prosthesis (Gallagher et al, 2010). The three subscales of the Activity Restriction domain are referred to as TAPES-AR and the functional subscale of the Satisfaction domain is referred to as TAPES-FUN. Only the TAPES-AR domain and TAPES-FUN subscale are used in this protocol.

PROMIS Fatigue Short Form 7a

PROMIS item banks and their short forms are a reliable and precise measurements of patient reported outcome measures (Cella, 2005-2008). The PROMIS Fatigue item banks assess a range of self-reported symptoms, from mild subjective feelings of tiredness to an overwhelming, debilitating, and sustained sense of exhaustion that likely decreases one's ability to execute daily activities and function normally in family or social roles. Fatigue is divided into the experience of fatigue (frequency, duration, and intensity) and the impact of fatigue on physical, mental, and social activities. The fatigue short forms are universal rather than disease-specific. All assess fatigue over the past seven days.

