Secondary Efficacy Endpoint #1: Level of walking endurance as measured by the distance walked in the six-minute walk test (6MWT) and the perceived exertion (RPE) measured by Borg CR100. No hypothesis will be tested. Instead, the percentage of subjects (along with the exact 95% binomial confidence interval) with either a clinically meaningful improvement in the distance walked in the six minute walk test or a clinically meaningful decrease in the rating of perceived exertion (RPE) while wearing the Revo-M foot compared to the everyday foot will be computed. A clinically-significant improvement in the 6MWT is defined as a change in distance of greater than 45 meters [Resnik 2011]. A clinically-significant improvement in the RPE is defined as a change greater than 10 points [Ries 2005].

Secondary Efficacy Endpoint #2: Perception of balance confidence as measured by the extended Activities-specific Balance Confidence (ABC) Scale. It is hypothesized that ABC scores will be higher for subjects when they are using the Revo-M compared to their everyday feet. In statistical terms the null and alternative hypotheses are as follows:

$$H_0: \mu_{\text{Revo-M}} \leq \mu_{\text{Everyday}}$$

$$H_A: \mu_{\text{Revo-M}} > \mu_{\text{Everyday}}$$

Where H_0 is the null hypothesis, $\mu_{\text{Revo-M}}$ is the mean ABC score using the Revo-M, μ_{Everyday} is the mean ABC score using the everyday feet and H_A is the alternative hypothesis indicating that balance confidence as measured by the ABC scale is greater for Revo-M than for everyday feet.

The hypothesis will be tested using a 2-sided Wilcoxon matched pairs signed ranks test. If the observed p-value is \leq the Hochberg adjusted critical value and the mean of PLUS-M scores using the Revo-M foot is greater than PLUS-M scores using the everyday feet, the null hypothesis will be rejected in favor of the alternative hypothesis and the superiority of the Revo-M will be supported.

Secondary Efficacy Endpoint #3: Level of functional satisfaction as measured by the TAPES Functional Satisfaction (TAPES-FUN) subscale. It is hypothesized that TAPES-FUN scores will be higher for subjects when they are using the Revo-M compared to their everyday feet. In statistical terms the null and alternative hypotheses are as follows:

$$H_0: \mu_{\text{Revo-M}} \leq \mu_{\text{Everyday}}$$

$$H_A: \mu_{\text{Revo-M}} > \mu_{\text{Everyday}}$$

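### The either/or responder rule for secondary endpoint #1 counts lower exertion as better walking endurance even when distance falls by more than 45 m, and the percentage has no reference rate

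*Combined protocol and SAP*

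**What the plan says.** Under Secondary Efficacy Endpoints, endpoint #1 is the level of walking endurance, built from six-minute walk distance and Borg CR100 exertion. The plan states "No hypothesis will be tested". The specified result is one percentage, reported "along with the exact 95% binomial confidence interval": the subjects who show "either a clinically meaningful improvement in the distance walked in the six minute walk test or a clinically meaningful decrease" in RPE on Revo-M compared with the everyday foot.

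The thresholds are:
- distance: "A clinically-significant improvement in the 6MWT is defined as a change in distance of greater than 45 meters"
- exertion: "A clinically-significant improvement in the RPE is defined as a change greater than 10 points"

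No condition is placed on the other component. No worsened percentage, expected rate or comparison rate is named.

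The section Six-minute walk test says "The walk test is patient self-paced and assesses the level of functional capacity" and "Patients are allowed to stop and rest during the test, however, the timer does not stop".

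Three other parts of the plan bear on this:
- Data Analysis provides descriptive summaries of change scores, with each variable analysed on its own.
- The Study Summary has the baseline assessments repeated on the everyday foot in Period IV.
- Exploratory Efficacy Endpoints compares Revo-M with the comparative feet and with the everyday foot at both time points, by signed-rank tests.

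**The concern.** There are two weaknesses, and they are separate.

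First, either component is sufficient alone. In a self-paced test a subject can lower exertion by walking more slowly or resting more. Someone who covers 60 m less and rates exertion 11 points lower meets the rule. The percentage therefore mixes two patterns: similar distance for less effort, which is a plausible benefit, and clearly less distance for less effort, which is hard to call better endurance.

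Second, each subject has two ways to qualify and only favourable changes are counted, so ordinary test-retest variation produces responders. The interval describes sampling error around the percentage. It does not say what percentage to expect if the foot made no difference.

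At stake is whether the one result specified for this endpoint can be read as evidence of improved endurance. The section on interim analysis and adaptive design foresees a possible pivotal trial that addresses secondary objectives and includes these subjects' data, so the definition may carry forward.

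**Working it through.** **Step 1: the rule as written (no assumptions).** A distance change of -60 m fails the distance arm. An RPE change of -11 passes the RPE arm, since 11 > 10. One arm is enough, so the subject is a responder. The same follows for any distance loss.

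**Step 2: what the interval can show.** Exact (Clopper-Pearson) 95% limits at the minimum sample size of 24, for illustrative counts:
- 1 of 24 (4%): 0.1% to 21%
- 6 of 24 (25%): 9.8% to 46.7%
- 8 of 24 (33%): 15.6% to 55.3%

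The lower limit is above zero with a single responder, so excluding zero says nothing about benefit. If the no-effect rate were 20%, the probability of 6 or more responders of 24 would be 0.34. If it were 30%, it would be 0.77.

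**Step 3: chance rate under no effect.** The plan gives no rate, SD or power for this endpoint, so there is no figure to reproduce. Assumptions:
- Let X be the change in distance and Y the change in RPE, bivariate normal with mean zero.
- SD of X (s1) is 30, 45 or 60 m. SD of Y (s2) is 8, 10, 15 or 20 points.
- The correlation of X with Y is -0.4, 0 or 0.4. A positive value means that walking further goes with more exertion.

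Formulas:
- p1 = P(X > 45) = 1 - Φ(45/s1)
- p2 = P(Y < -10) = 1 - Φ(10/s2)
- improved = p1 + p2 - P(X > 45 and Y < -10)
- discordant d = P(X < -45 and Y < -10)
- improved with the distance guard = improved - d

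At zero correlation both joint probabilities equal p1 × p2:
- s1 = 30, s2 = 8: p1 = 1 - Φ(1.5) = 0.0668; p2 = 1 - Φ(1.25) = 0.1056; product 0.0071. Improved = 0.0668 + 0.1056 - 0.0071 = 0.165; d = 0.007.
- s1 = 60, s2 = 20: p1 = 1 - Φ(0.75) = 0.2266; p2 = 1 - Φ(0.5) = 0.3085; product 0.0699. Improved = 0.2266 + 0.3085 - 0.0699 = 0.465; d = 0.070.

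Range over the grid, using the bivariate normal distribution function where the correlation is not zero:

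| Correlation of X with Y | Improved, rule as written | Discordant (loss > 45 m, RPE drop > 10), % of all subjects | Improved, with guard |
|---|---|---|---|
| -0.4 | 15.2-41.9% | 0.1-3.1% | 15.1-38.8% |
| 0 | 16.5-46.5% | 0.7-7.0% | 15.8-39.5% |
| 0.4 | 17.1-50.5% | 2.0-11.6% | 15.1-38.8% |

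In a study of 24, the largest discordant share is 0.116 × 24 = 2.8 subjects. With smaller SDs, about 27 m and 6 points, the either/or rate falls to about 9-10%.

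**Step 4: what the guard does and does not do.** It removes the discordant subjects. It leaves a chance rate of about 15-40%, so it does not supply a benchmark. The mirror-image percentage does: with no effect and symmetric changes, the worsened and improved percentages have the same expectation.

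**The case against.** The strongest defence is that the endpoint is descriptive, with no test, success criterion or superiority claim, in a study whose analysis is mainly descriptive. A reader might infer that a loose rule threatens type I error, since the Hypothesis section counts three secondary endpoints in one Hochberg family. The endpoint's own text rules that out, because it produces no p-value.

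Next, the either/or form has a rationale. In a self-paced test, benefit may show as more distance or as less effort. A reader might infer that the endpoint does not measure walking endurance at all. The documents do not support that: on the assumptions above, responders with a meaningful distance loss are a minority in every setting.

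The plan also helps in part. The change-score summaries under Data Analysis would show a general slowing, and the exploratory tests use the comparative feet and Period IV. However, these are summaries or tests of each measure singly. They do not show how many responders lost distance, give a worsened percentage, or provide a same-foot responder rate.

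Finally, a reader might treat a gain above 45 m with much higher exertion as an equally false response. Nothing in the documents says that a meaningful gain in distance should be void because exertion rose. That is a choice for the sponsor.

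What stands of the defence limits the weight of the point. It does not remove the misclassification or the missing reference rate.

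**Conclusion.** The point holds in a limited form. That the rule counts a subject with a distance loss over 45 m as improved follows from the text and needs no assumption. So does the absence of a worsened or same-foot rate.

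The size does rest on assumptions, because the documents give neither SDs of change nor a correlation for the two measures. With no true effect, SDs of 30-60 m and 8-20 points, and correlation -0.4 to 0.4, about 15-50% of subjects would be responders by chance. About 0.1-12% of all subjects would be RPE responders with a loss over 45 m. Counting RPE responders who walked any shorter distance gives a larger share, but that includes trivial losses and should not be read as the size of this problem.

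The missing reference rate matters more for interpretation than the discordant cases do. Neither affects type I error. The change is worth making because it costs little and the percentage is the only result specified for this endpoint.

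**What to change.** In the text of secondary endpoint #1:

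1. Do not count an RPE decrease of more than 10 points as a response when distance falls by more than 45 m.
2. Report the mirror-image worsened percentage, with its exact interval, beside the improved percentage. Worsened means a distance loss of more than 45 m, or an RPE rise of more than 10 points unless distance rises by more than 45 m. With the guard in item 1, no subject can fall in both groups.
3. Report the responder rate for each component and the number of discordant subjects.

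Optionally, apply the same rule to the everyday foot, Period IV versus the end of Period I, as a same-foot benchmark.

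The cost is SAP wording and a few table rows, with no new visits or measurements. The responder percentage will be slightly lower, by the discordant share in the table above. Whether to exclude distance gains that come with higher exertion is a matter of choice and is not part of this change.
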